8.2 SUBJECT CHARACTERISTICS

The number of patients enrolled in the study, number withdrawn, and reasons for withdrawal shall be summarized.

- Demographics: Subject demographic data will be summarized for the entire study population. Demographic variables will include:
 - Sex
 - Age (years) as a continuous measure and categorized (N, %) by the following age groups:
 - 2 – 5 years
 - 6 – 21 years
 - 22 – 59 years
 - ≥ 60 years

090177e19dd636e3\Approved\Approved On: 25-Jun-2023 03:44 (GMT)

- Unknown
- Race categorized as: American Indian/Alaska Native, Asian, African American/Black, Caucasian/White, Native Hawaiian/Pacific Islander, Other, Unknown, or Refused.
- Ethnicity categorized as: Hispanic or Latino, Not Hispanic or Latino, Other, Unknown, or Not provided.
- Education Level
- Employment status
- Household Income

8.3 DATA ANALYSIS

All summaries and analyses should be presented in tabular or graphical form.

➤ Analysis Sets

There will only be one analysis set consisting of samples with valid Lucira COVID-19 & Flu Test results and valid reference results. Valid Lucira COVID-19 Test results may be positive or negative for COVID-19. The percentage of the expected result shall be computed individually along with the associated 95% Wilson Score Confidence Interval for each set.

For all invalid Lucira COVID-19 & Flu Test results, one additional specimen collection should be attempted, and the Lucira COVID-19 & Flu Test should be re-run with a new Test Kit. If specimen recollection leads to a valid Lucira COVID-19 & Flu Test result, that valid retest result should be reported. If the Lucira COVID-19 & Flu Test result is "Invalid", then this test result shall be considered completely invalid and therefore non-evaluable.

➤ Prevalence Rate / Expected Values

Study prevalence of SARS-CoV-2 and Influenza A&B should be summarized by counts and percentages

➤ Collection Performance/ Incidence Rate

Relevant study observations should be summarized by counts and percentages:

- Self-Collection
- Assisted Collection

➤ Missing Values

Missing values should not be imputed for any of the study assessments.

➤ Data Exclusions

The following shall result in subjects being removed from final data analysis:

- Subject withdrawals
- Subject does not meet inclusion/exclusion criteria
- Swab specimens were not processed according to protocol
- Missing results
- Excluded by an Event

This analysis should be presented across all study sites and by individual study site.

➤ Efficacy Analysis

Sensitivity and specificity along with their associated 2-sided Wilson Score 95% Confidence Intervals will be estimated for SARS-CoV-2 and Influenza A&B on the Lucira COVID-19 All-In-One Test in comparison to the reference test using the formulas below and a 2 x 2 contingency table ([Table 13.1](#)).

090177e19dd636e3\Approved\Approved On: 25-Jun-2023 03:44 (GMT)

Positive Percent Agreement: $a/(a+c) \times 100$

Negative Percent Agreement: $d/(b+d) \times 100$

Table 13.1: 2 x 2 table for calculation of positive percent agreement and negative percent agreement:

	Reference Positive	Reference Negative	Row Totals
Lucira Positive	a	b	a+b
Lucira Negative	c	d	c+d
Column Totals	a+c	b+d	a+b+c+d

➤ **Invalid Rate**

The initial invalid rates and unresolved invalid rates should be estimated for the Lucira COVID-19 & Flu Test.

090177e19dd636e3\Approved\Approved On: 25-Jun-2023 03:44 (GMT)

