3.2 INTENDED USE

The Lucira COVID-19 & Flu Test is a single use real-time RT-LAMP test kit intended for simultaneous rapid qualitative detection and differentiation of RNA from SARS-CoV-2, Influenza A, and Influenza B virus from self-collected anterior nasal (nasal) Swab specimens, in individuals aged 14 years and older (self-collected), or individuals ≥ 2 years (collected by an adult) suspected of respiratory viral infection consistent with COVID-19, Influenza A, and/or Influenza B. Clinical signs and symptoms of respiratory viral infection due to SARS-CoV-2 and influenza can be similar. The Lucira COVID-19 & Flu Test is intended for use as an aid in the differential diagnosis of SARS-CoV-2, Influenza A, and Influenza B, in humans, and is not intended to detect Influenza C.

The SARS-CoV-2, Influenza A, or Influenza B RNA is generally detectable in nasal Swab samples during the acute phase of infection. Positive results are indicative of the presence of SARS-CoV-2, Influenza A, or Influenza B RNA; clinical correlation with patient history and other diagnostic information is necessary to determine patient infection status. Positive results do not rule out bacterial infection or co-infection with other viruses. The agent detected may not be the definite cause of disease.

Persons who test positive with the Lucira COVID-19 & Flu Test should seek follow up care with their physician, or healthcare provider, as additional testing and public health reporting may be necessary.

Negative results do not preclude infection from SARS-CoV-2, Influenza A, and/or Influenza B and should not be used as the sole basis for treatment or other patient management decisions. Negative results must be combined with clinical observations, patient history, and epidemiological information.

This Lucira COVID-19 & Flu Test is intended for self-testing in a non-laboratory setting, or for home use.

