6.2 EXCLUSION CRITERIA

1. Currently suffering from nasal trauma such as a nosebleed
2. Received a nasal rinse/wash/aspirates for standard of care testing
3. The subject is undergoing treatment for COVID-19 or Flu currently and/or within the past 14 days of the study visit, including but not limited to: inhaled influenza vaccine (FluMist®) or flu antiviral medication, which may include but is not limited to Amantadine (Symmetrel®), Rimantadine (Flumadine®), Zanamivir (Relenza®), Oseltamivir (Tamiflu®), or Baloxavir marboxil (Xofluza®).
4. The subject is currently receiving or has received within the past 30 days of the study visit an experimental biologic, drug, or device including either treatment or therapy.
5. The subject has previously participated in this research study
6. Incorrect comparator swab type or transport media
7. Incorrect specimen handling
8. Subjects not consented

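### Section 8.3's mandatory exclusions could be read to drop valid result pairs because a lay user departed from the QRI; the plan should settle their scope and have exclusions decided without sight of results

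*Combined protocol and SAP*

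**What the plan says.** Section 8.3 (Analysis Sets): "There will only be one analysis set consisting of samples with valid Lucira COVID-19 & Flu Test results and valid reference results". For an invalid Lucira result the swab is retaken once: "If specimen recollection leads to a valid Lucira COVID-19 & Flu Test result, that valid retest result should be reported".

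Section 8.3 (Data Exclusions) then lists grounds that must lead to removal from the final analysis. Three matter here:

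- "Swab specimens were not processed according to protocol".
- Failure of the inclusion/exclusion criteria. Through this bullet, section 6.2 criterion 6, "Incorrect comparator swab type or transport media", and criterion 7, "Incorrect specimen handling", become analysis exclusions.
- "Excluded by an Event", with no statement of which events qualify.

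On use by lay persons, section 3.2 says the test "is intended for self-testing in a non-laboratory setting, or for home use". Sections 5.1 and 7.3 have the participant collect the swab and run the test by the QRI. Section 7.3.2 has the health care professional (HCP) record departures from the QRI and attaches no analysis consequence to them. Section 8.3 (Collection Performance) says, for self- and assisted collection: "Relevant study observations should be summarized by counts and percentages".

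Section 9.1.8 requires deviations that lead to data exclusion to appear in the final report.

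**The concern.** Collection and running errors by lay users are part of what a home-use test is up against, and the study simulates home use in order to measure performance under those conditions. Sections 5.1 and 7.3 make use of the QRI a study procedure, so a departure from it can be taken as a departure from protocol. On that view, a pair with two valid results leaves the only analysis set because the user made a mistake. If such mistakes produce false negatives, those pairs come out of cell c in the formula PPA = a/(a+c), and the reported figure describes QRI-compliant use rather than lay use.

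Two analysts could follow this plan in good faith and report different PPAs. The choice can also be made with results in view. Site staff both record deviations and read the Lucira result (sections 5.1, 7.3, 7.3.2), reference results are supplied daily (9.1.4.2), and the sponsor compiles both (9.1.4.3). Nothing requires exclusions to be settled before or apart from the results.

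The point is confined to collection and running errors. Staff interpret the result in this study, so errors in reading it by the user do not arise. No bias in negative percent agreement (NPA) is claimed.

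**Working it through.** **Scope of the rules.** Text that favours a broad reading:

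- Criterion 6 names the comparator; criterion 7, directly below it, names neither a specimen nor an actor.
- The 8.3 rule refers to swab specimens in general, and 8.3 itself uses the word specimen for the Lucira swab in its retest rule.
- Sections 5.1, 7.3 and 7.3.2 tie the participant's swab and test to the QRI and have departures recorded.

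Text that favours a reference-only reading:

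- Section 7.3.5 speaks of processing specimens when it describes shipment to the reference laboratory.
- Section 9.1.4.1 speaks of specimen handling when it describes cold storage of the reference specimen.
- Section 7.3.2 only documents QRI departures; its remedy for a contaminated swab or an invalid test is a new sample on a new device.
- The analysis set is defined by valid results, and collection observations are tabulated as an outcome.

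No sentence limits the mandatory list, so the scope stays open.

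**What could turn on it.** The plan gives no user-error rate, no exclusion rate and no assumed true PPA, so there is no plan figure to reproduce. Inputs from the documents: target positives of 50 Flu A, 30 Flu B and 120 COVID-19 (8.1); PPA goals of 90% for flu and 80% for COVID-19 (section 4); two-sided 95% Wilson intervals (8.3). Starting counts are chosen just below the goal and every excluded pair is taken to be a miss. The cases therefore show the fewest exclusions that could matter, not a likely effect.

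*Goals read as point estimates (assumption).*

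| Target | All pairs (95% CI) | One miss removed | Two misses removed (95% CI) |
|---|---|---|---|
| Flu A | 44/50 = 88.0% (76.2–94.4) | 44/49 = 89.8% | 44/48 = 91.7% (80.4–96.7) |
| Flu B | 26/30 = 86.7% (70.3–94.7) | 26/29 = 89.7% | 26/28 = 92.9% (77.4–98.0) |
| COVID-19 | 95/120 = 79.2% (71.1–85.5) | 95/119 = 79.8% | 95/118 = 80.5% (72.4–86.6) |

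One exclusion changes no verdict; two can. If the two Flu A pairs removed were one miss and one agreement, the result would be 43/48 = 89.6%, still below 90%.

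*Goals read as Wilson lower limits (alternative assumption).* The cases in the table fail before and after. From other starting counts, one excluded miss can be enough: Flu A 49/50, lower limit 89.5%, becomes 49/49, 92.7%; COVID-19 104/120, 79.4%, becomes 104/119, 80.2%. Flu B cannot pass even at 30/30 (88.6%).

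*Range.* Let e be the share of reference positives excluded, g the PPA among those kept and r the PPA among those excluded. The all-pairs PPA is (1 − e)g + er, so the overstatement is g − [(1 − e)g + er] = e(g − r). Take g at the goal, with assumed r = 50% and e = 2%, 5% and 10%:

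- Flu: 0.02 × 40 = 0.8, 0.05 × 40 = 2.0 and 0.10 × 40 = 4.0 percentage points.
- COVID-19: 0.02 × 30 = 0.6, 0.05 × 30 = 1.5 and 0.10 × 30 = 3.0 percentage points.
- If r = g, the overstatement is zero.

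**The case against.** The strongest reply is that the plan never meant to exclude user error. It does not use processing for what the participant does: that swab is collected, tested and then discarded. The operational uses of processing and handling concern reference specimens. QRI departures are recorded without any removal attached, valid results define the analysis set, and collection observations have their own summary. This stands, and it makes the reference-only reading plausible. A reader might infer that the rules taken literally require valid pairs with a user deviation to be dropped; the documents do not support that. Removal is one possible reading.

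Transparency also counts for the plan. Section 9.1.8 has deviations that cause exclusion reported, site data are entered daily (9.1.4.1), deviations are reported within 2 working days, and study events go on an Unanticipated Event Form. A reader of the final report should therefore see these exclusions. But reporting them does not restore the pairs to the estimate, and the form does not say which events exclude.

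The figures are constructed: the starting counts are picked, every excluded pair is a miss, and the exclusion rates and the 50% PPA are assumed. That is right, and they carry no weight as evidence that bias will occur. Result-masked decisions go beyond curing the ambiguity, but they address a gap that remains under either reading.

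**Conclusion.** The concern holds as an unresolved scope with a possible bias. The mandatory exclusions could be read to remove valid pairs for a lay user's QRI departure. No text settles this, no analysis with excluded pairs restored is planned, and exclusions, including those for unspecified events, may be decided with results known.

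Overstated PPA needs two further conditions: the broad reading is applied, and user errors cause misses. The documents show neither. The size is unknown and may be zero; under the assumed rates it is 0.8–4.0 points for flu and 0.6–3.0 points for COVID-19. With so few target positives, two excluded misses could carry a point estimate across its goal, but only from a start just below it. The lower-limit cases rest on a success rule that the plan does not state.

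A reader might also infer that exclusions will be chosen to favour the device. Nothing in the documents suggests this; the plan merely lacks a safeguard. The point is worth fixing, with medium confidence.

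**What to change.** 1. State in section 8.3 and in criterion 7 of section 6.2 that a QRI deviation by the participant or the assisting adult is not a ground for exclusion, so that pairs with valid Lucira and valid reference results stay in the primary PPA/NPA analysis. Show the QRI-compliant subset as a sensitivity analysis.
2. Keep both rules for errors by site staff or the laboratory.
3. State which events exclude a subject.
4. Require every exclusion to be decided and documented without sight of whether the Lucira and reference results are positive or negative, for example by someone working from the deviation listing with results hidden.

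The cost is a few sentences, one extra table and a short masked review of the deviation listing. No new data are needed, because QRI deviations are already recorded. The downside is a headline PPA that may be slightly less favourable. If the sponsor already intends the narrow reading, items 1 and 2 only put it in writing.

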9 SUPPORTING DOCUMENTATION AND OPERATIONAL CONSIDERATIONS

9.1 REGULATORY, ETHICAL AND STUDY OVERSIGHT CONSIDERATIONS

9.1.1 INFORMED CONSENT PROCESS

Upon receiving IRB approval, the Investigator must receive IRB-approved informed consent and the letter from the IRB granting approval. The letter(s) must clearly state the version of the protocol and the informed consent that they have approved as well as any other documents, such as advertisements or other materials, they may have been reviewed and approved.

Before recruitment and enrollment into the study, each prospective candidate shall be given a full explanation of the nature and purposes of the study and a copy of the IRB-approved informed consent form to review. Once the essential study information has been provided and the Investigator is assured that each individual volunteer understands the implications of participating in the study, the subject will be asked to give consent to participate in the study by signing the informed consent form. The consent forms shall be signed and dated by the appropriate parties. The subject will be given a copy of the signed informed consent form.

9.1.2 STUDY DISCONTINUATION AND CLOSURE

If Lucira Health or its representative, the Investigator, or any national regulatory officials discover conditions during the study that indicate that the study, site or intended use operator should be terminated, this action may be taken after appropriate consultation between Lucira Health, its representative, and the Investigator. The study may be terminated prematurely by the Principal Investigator or his/her designee and Lucira Health if:

- The number and/or severity of AE justifies termination of the study
- The discovery of an unexpected, serious, or unacceptable risk to enrolled subjects
- New data becomes available which raise concern about the safety of the study device, such that continuation might cause unacceptable risk to subjects

- The study may be terminated at an individual site and another site sought if there is a failure to recruit enough subjects for the study
- The decision on the part of Lucira Health to suspend or discontinue testing, evaluation, or development of the study device
- Failure of the Investigator to comply with pertinent regulations
- Submission of knowingly false information from the research facility to Lucira Health, Monitor or any regulatory officials
- Insufficient adherence to protocol requirements

In addition, the Sponsor reserves the right to discontinue the study, but intend only to exercise this right for valid scientific or administrative reasons.

After such a decision, written notification must be sent to the IRB along with any IRB-required filings. Study termination and follow-up will be performed in compliance with the conditions set forth in GCP requirements.

9.1.3 CONFIDENTIALITY AND PRIVACY

Confidentiality

During the enrollment process, each subject will be given a unique identifier to ensure anonymity. All study-related materials, specimens, documents, and data held by the Sponsor will refer to the subject's unique subject ID. Any data that may be published in internal reports, abstracts, scientific journals, or presented at medical meetings will reference a unique subject code and will not reveal the subject's identity. At no time should any data forms or specimens be marked with the subject's name or any other traceable identifier. The informed consent form (ICF), which contains the subject's name, will be kept separately at the patient enrollment sites in a secure locked location. At no time will the original or a copy of the ICF revealing the subject's name be distributed outside of the patient enrollment site research team.

Disclosure of Data

All information obtained during the conduct of this study will be regarded as confidential and written permission from Lucira Health is required prior to disclosing any information relative to this study.

Data Access

The Investigator and the Investigators' designated staff personnel will have access to the following subject data: Name or Initial, and previous research record.

The study monitor, other authorized representatives of the sponsor, representatives of the Institutional Review Board (IRB), or regulatory agencies may inspect all documents and records required to be maintained by the investigator.

9.1.4 KEY ROLES AND STUDY GOVERNANCE

9.1.4.1 CANDIDATE DEVICE TESTING SITES

- Provide a simulated Home Use Environment (e.g., table free of clutter, sink, clock, lamp, etc.)
- Identify suitable subjects for enrollment
- Assign study subject identification numbers

090177e19ddd636e3\Approved\Approved On: 25-Jun-2023 03:44 (GMT)

- De-identify Protected Health Information (PHI) from potential respiratory research participants specimens
- Sites shall provide de-identified source documentation that provides subject demographics and test results
- Collect comparator nasal swabs by a qualified health care professional
- Specimen handling - Prospective fresh reference method specimen shall be stored and transferred at 2-8°C
- Comparator specimens shall be shipped daily to the designated lab
- Study data EDC entries shall be completed daily

9.1.4.2 REFERENCE METHOD TESTING SITE

- Document the receipt of clinical specimens
- Designate operators to perform reference method testing
- Perform reference method testing on enrolled samples to obtain qualitative results
- Study data results shall be provided daily

9.1.4.3 STUDY SPONSOR

- Provide investigational product and materials to the investigative sites for Lucira investigational testing
- Ensure that the site staff receive appropriate training to conduct the study
- Monitor the study activities through on-site visits, remote visits, or other means (e.g., phone calls, emails)
- Review and compile study data received from the candidate device and reference method testing sites

9.1.5 CLINICAL MONITORING

The task of the study monitor is to ensure the acceptable conduct of the study through frequent contacts by phone, email, and in person with the responsible Investigator/designee, in accordance with the Sponsor's or its representative's internal procedures.

Lucira Health will monitor study progress in accordance with the protocol and applicable regulations. To ensure equal distribution of enrolled subjects based on FDA EUA guidance and satisfy specificity requirements, enrollment will be closely monitored. Lucira Health personnel or designee may perform an audit at any time during or after completion of the study, and all data pertaining to a subject's participation and all study-related documentation in this investigation must be made available. In addition, a representative from a regulatory authority may choose to inspect a study site at any time prior to, or after completion of the clinical study. All pertinent study data shall be made available to the regulatory authority for verification, audit, or inspection purposes.

When the enrollment goal is reached, Lucira Health or its representative will notify the sites the study is complete.

The duration of the study is expected to be at least 12 weeks. When the study is ready to be terminated, a Site Closeout Visit shall be conducted. Sites will be instructed on the disposition of unused investigational materials by Lucira Health or its representative at that time. Study documents will be checked for completeness and filed. The Investigator will allow Lucira Health and/or its representative and/or any regulatory authority to inspect all CRFs and study-related documents to verify the study was performed according to protocol. Monitors will review informed consent forms for completeness as well as verify source documentation.

090177e19dd636e3\Approved\Approved On: 25-Jun-2023 03:44 (GMT)

To ensure the accuracy of data, direct access to source data by the Sponsor, its representative, and regulatory authorities is mandatory. Direct access to source data may be required to perform de-identified analysis both during and after the study. The Sponsor reserves the right to terminate the study for refusal of the Investigator/Institution to supply source documentation of work performed in the study.

9.1.6 QUALITY ASSURANCE AND QUALITY CONTROL

Lucira Health is responsible for the training, organization, monitoring supply of study materials, and quality assurance for the clinical study. Prior to the start of this study all study staff shall be trained on the protocol, roles and responsibilities, data management and regulatory requirements.

